## Inclusion and exclusion criteria

- Inclusion criteria
  - o Mother / birthing parent aged 16 or over.
  - o Mother / birthing parent must have parental responsibility for baby
  - o Mother / birthing parent is registered with a GP in England
  - o Singleton birth

For those with complicated births or early postnatal periods, for example where admission to NICU is necessary, final sampling decisions will be made on a case-by-case basis at the discretion of the research staff and with the NHS clinical team - as well as consent from the parent(s). Births from an egg or sperm donor are eligible, provided the pregnant person will also have full parental responsibility.

- Exclusion criteria
  - Mother / birthing parent under 16
  - Mother / birthing parent who will not have parental responsibility for the baby (Babies who are being adopted)
  - o Mother / birthing parent lacking capacity to provide informed consent for any reason
  - o Mother / birthing parent who do not give birth in one of the recruiting hospitals
  - o Mother / birthing parent who do not have an NHS number
  - o Mother / birthing parent who is serving time in prison

In the initial rollout of the study we will exclude multiple births. We will seek to include these in the study as soon as our core processes are established and we feel the processes are robust enough to support them.

# Sample size

Determination of sample size was aligned to the primary outcome of the study, to determine clinical utility of genomic newborn screening, and focusing on one component of it - evidence of the potential incidence range of genetic diseases where early intervention is likely to improve outcomes in newborns in the UK population. As set out in Sections 6 and 13 in more detail, the primary outcome is one of a suite of strands of evidence that the study aims to generate to support policy decisions in this area.

The work carried out by the Genomic Analysis in Children Task and Finish Group estimates that between 1 in 457 and 1 in 686 live births would be affected by a disorder that:

- Is not part of current newborn screening
- Has a treatment available within the first five years of life that impacts substantially on mortality or morbidity

The required number of participants to be 95% certain that the incidence estimate from the study will be between the middle point of an estimate, 1/572 +/- 6% error, is approximately 105,000.

The sample size calculation to estimate this incidence of genetic diseases was based on the normal approximation to the binomial distribution with simple random sampling assumed . For the sample size calculations the proportion of subjects screened positive was assumed to be 0.011, and it was derived from an estimate of the true population incidence, the middle point of the estimate, 1/572, by using the sensitivity of detection of 65% and specificity of detection of 99% . Dropout rate was assumed to be 10%. The sensitivity of detection of 65% and specificity of detection of 99% used in calculations is the lower bounds of the estimates obtained during bioinformatics prioritisation algorithm modelling. Expected specificity is discussed in more detail in Section 10. We note that sample size calculations for estimating prevalence in rare conditions are highly sensitive to the assumptions of test performance metrics, in particular the assumption on specificity . Therefore we will update the calculations before the study, when the list of conditions is finalised and sensitivity and specificity modelling for those conditions is complete, as well as monitor and update throughout the study. In addition, throughout the study we will be updating the calculations to monitor that the sample size is sufficient to evaluate expected study-wide true positive rate. See section 13 for more information.

To validate the sample size calculations further and to understand the behaviour of sample size in relation to other parameters, Monte Carlo simulations using a range of true population incidence, sensitivity and specificity were performed. An example of simulation, assuming 65% sensitivity, 99% specificity and 1/572 true incidence is depicted in Figure 5.

Figure 5 - An example of the Monte Carlo simulation of two-sided 95% confidence interval for the proportion of subjects screened positive assuming 99% specificity and 65% sensitivity. For each value in the sample size, the expected proportion of subjects screened positive was computed from a binomial distribution 15 000 times. The final confidence interval is obtained by clipping 95% of the values among the 15 000 (filled area). The dashed lines show the maximum and minimum values of the obtained proportion of subjects screened positive for each sample size. The dotted lines indicate the expected proportion of subjects screened positive +/- 6% error margin.

[figure not shown]

Figure 5 - An example of the Monte Carlo simulation of two-sided 95% confidence interval for the proportion of subjects screened positive assuming 99% specificity and 65% sensitivity.

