#### Interim Analysis

This interim analysis will allow for decisions and adjustments - for example to recruitment materials, sampling strategy, the stringency of variant prioritisation filtering, adjusting variant inclusion or exclusion lists, adjustments to the conditions/genes list and study continuation.

We expect to perform interim analyses when the first 1,000 participants' data is processed, then at 5,000, 20,000 and 50,000. These points may be adjusted and made more frequent, especially in the initial stages of the study, if deemed necessary e.g., if significant changes to variant prioritisation approach are implemented and the impact of that needs assessment.

The main focus of the interim analysis will be to assess:

- recruitment profile including crude recruitment rates as a proportion of births at recruiting sites and the diversity of recruitment as compared to the diversity of the birthing population at recruiting sites sourced from the Maternity Services Data Set
- apparent true positive and false positive numbers and their ratio overall, for individual genes/conditions and by participant ethnicity so that we can:
  - adjust bioinformatics and interpretation approach to variant reporting, including stringency of variant filtering strategy, thresholds and adjustment to variant inclusion and exclusion lists
  - o re-evaluate the sample size calculations required to achieve the primary study outcome. This analysis will re-evaluate sample size required for the incidence estimate, as described in Section 6, using real world study data, as well as sample size required to achieve the expected number of screen-identified true positive diagnoses in the study. The true positives for this analysis will be defined as newborns with pathogenic or likely pathogenic variants identified and reported through genomic screening, and diagnosis confirmed by orthogonal testing (e.g., biochemical tests). The expected number of true positives will be updated when the conditions to be screened list is finalised.

The data on true positives and false positives will be obtained from the results of confirmatory testing for participants with "condition(s) suspected" results. We will also collect data on false negatives from linked longitudinal health data and incorporate it into interim analysis.

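### The ±6% precision promised for the incidence of 1/572 is the precision of the proportion screened positive; the incidence itself would be known to between about ±15% and ±60%, depending on the estimator

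*Protocol*

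**What the plan says.** Under Sample size, Section 6 of the protocol bases the study size on the incidence of treatable conditions outside current newborn screening, put at between 1 in 457 and 1 in 686 live births. About 105,000 participants are said to be needed to be "95% certain that the incidence estimate from the study will be between the middle point of an estimate, 1/572 +/- 6% error".

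The next paragraph describes the calculation. It is "based on the normal approximation to the binomial distribution with simple random sampling assumed", and "For the sample size calculations the proportion of subjects screened positive was assumed to be 0.011". That proportion is obtained from 1/572 with 65% sensitivity and 99% specificity, and dropout is set at 10%. The Figure 5 legend describes a simulated "two-sided 95% confidence interval for the proportion of subjects screened positive assuming 99% specificity and 65% sensitivity" and adds: "The dotted lines indicate the expected proportion of subjects screened positive +/- 6% error margin".

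Section 13, Interim Analysis, carries the method forward: "This analysis will re-evaluate sample size required for the incidence estimate, as described in Section 6". The same sentence adds a second check, on the sample size needed to reach the expected number of true positives confirmed by orthogonal testing.

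**The concern.** The incidence (1/572 = 0.00175) and the proportion screened positive (0.011) differ more than sixfold, and most of the second is false positives. A 6% margin on one is not a 6% margin on the other. Section 6 never converts the margin back to incidence, and it gives no incidence precision other than 6%.

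Two things are at stake. A policy reader of Section 6 will expect the incidence to within 6%. And an interim re-evaluation that repeats the Section 6 formula would respond to specificity in the wrong direction.

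**Working it through.** **Inputs (Section 6, Sample size).** Incidence π = 1/572 = 0.001748; sensitivity Se = 0.65; specificity Sp = 0.99; relative margin 6%; two-sided 95% (z = 1.96); dropout 10%, so 105,000 × 0.9 = 94,500 evaluable. The alternative Sp = 0.995 is the value that Section 10 (modelling of variant prioritisation) considers achievable.

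**1. Reproducing 105,000.**
- Proportion screened positive: p = Se·π + (1 − Sp)(1 − π) = 0.65/572 + 0.01 × 571/572 = 0.001136 + 0.009983 = 0.01112.
- n = z²(1 − p)/(0.06² p) = 94,906; divided by 0.9, 105,451. With p rounded to 0.011 the result is 95,943, or 106,603 after dropout. Either matches the stated figure.
- Applying 6% to π instead, even with a perfect test: n = z²(1 − π)/(0.06² π) ≈ 609,000, or about 677,000 after dropout. This does not match.

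So the 6% was applied to p. True positives make up 0.001136/0.01112 = 10% of p.

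**2. Converting to incidence.** The Rogan-Gladen estimator is π = (p + Sp − 1)/(Se + Sp − 1), so with Se and Sp known a half-width on p is divided by Se + Sp − 1 = 0.64.
- Half-width on p at 94,500: 1.96 × √(0.01112 × 0.98888/94,500) = 0.000669, which is 6.0% of p.
- On incidence: 0.000669/0.64 = 0.001045, which is 59.8% of 1/572. The interval is about 1/1,421 to 1/358.
- If all 105,000 were evaluable: ±57%.
- At Sp = 0.995 and 94,500: ±8.1% on p and ±44% on incidence.

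**3. Other estimators at 94,500.**
- Confirmed true positives, Se fixed at 65%: expected count 94,500 × 0.65/572 = 107; 1.96/√107.4 = ±19%.
- Perfect test: expected count 94,500/572 = 165; about ±15%.

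**4. What the Section 6 formula does when specificity changes** (6% held on p, 10% dropout):

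| Specificity | p | Babies required |
|---|---|---|
| 98% | 0.0211 | about 55,000 |
| 99% | 0.0111 | about 105,000 |
| 99.5% | 0.0061 | about 192,000 |

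The formula asks for fewer babies as the test gets worse, because extra false positives make p larger and easier to estimate in relative terms.

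**5. Can the study still separate the ends of its starting range?** Expected confirmed true positives at Se = 65% are 94,500 × 0.65/457 = 134 and 94,500 × 0.65/686 = 90. Assigning counts of 110 or fewer to the lower incidence misclassifies under 2% in each direction (exact Poisson).

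**The case against.** The protocol is open about its calculation. Section 6 and the Figure 5 legend both name the proportion screened positive. Section 6 also warns that such calculations are highly sensitive to specificity and promises updates. Incidence is described as only one component of the primary outcome. All of this is true, but none of it tells the reader that ±6% is not the incidence precision.

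A reader might infer from the ±60% that the study cannot refine the range 1/457 to 1/686. The documents do not support that. The ±60% belongs to an estimator that subtracts assumed false positives from raw screen positives, and the protocol does not name it as the final analysis. Section 13 plans Bayesian modelling, takes true and false positives from confirmatory testing and collects false negatives from linked records. Step 5 shows that confirmed counts can separate the two ends if sensitivity is reasonably well known. For the same reason, calling the stated precision ten times too optimistic fits the back-conversion only; against confirmed counts the factor is about three.

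A reader might also infer that the interim re-evaluation rests on the Section 6 formula alone. It does not, since the confirmed-true-positive check sits beside it. Nor is the gap the same at every specificity: with sensitivity fixed, it closes as specificity approaches 100%, where both margins are about ±19%.

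The Monte Carlo work does not rescue the statement as far as it is described: the one example shown concerns the proportion screened positive. Other runs are mentioned without detail, so nothing firmer can be said about them.

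**Conclusion.** The point holds as an error in the stated precision. The ±6% in Section 6 is the precision of the proportion screened positive and not of the incidence. Under the protocol's own inputs, 94,500 evaluable babies give about ±60% by back-conversion at 99% specificity, ±44% at 99.5%, about ±19% from confirmed true positives and about ±15% with a perfect test. None of these attains ±6%.

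The figures assume simple random sampling, 10% dropout and an incidence of 1/572. The back-conversion takes sensitivity and specificity as known, and the ±19% fixes sensitivity at 65%; uncertainty in either would widen them. The finding is no evidence that the study is too small for its purpose.

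**What to change.** **Section 6.** State that ±6% refers to the proportion screened positive. State the incidence precision separately and name its estimator: confirmed true positives plus ascertained false negatives, over babies with a result. The planning figure is about ±19% with sensitivity fixed at 65%, and wider when sensitivity is uncertain.

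**Section 13, Interim Analysis.** Base the incidence part of the sample size re-evaluation on that estimator and not on the Section 6 formula. Keep the confirmed-true-positive check already planned there.

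Section 2 needs no change, because it gives the sample size without the ±6%. The cost is a wording amendment to two sections and a less favourable published figure. The confirmatory results and the false-negative follow-up are already planned, and no extra babies are needed.

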For autosomal recessive genes, the specificity after manual curation reached 99.8%. The lower specificity for autosomal dominant genes (98.2% before manual curation) was heavily driven by a small number of genes with a large number of pathogenic or likely pathogenic variants in ClinVar, with just two genes accounting for 25% of samples, and 15 genes accounting for 70% of the samples with P/LP variants. Upon inspection, none of those genes are likely to pass conditions framework principles to be included in the programme. Although many of the autosomal dominant genes will not pass conditions selection by failing principles because of low penetrance and/or age of onset, our specificity modelling will feed into analytical validity assessment and the genes that present a risk of materially reducing study-wide specificity will not be included.

We also note, that for a small number of individuals, where relevant phenotype data was available in the National Genomic Research Library, we were able to confirm the presence of the condition, and thus reclassify them as true positives, however we did not include those into the assessment, because the phenotype data was not available for the majority of individuals.

Based on this preliminary analysis, we estimate that the study-wide (i.e. for all genes combined) specificity of 99.5% or higher is achievable. The estimate of 99.5% specificity, assuming 65% sensitivity and study-wide conditions prevalence of 1:575. Reducing the gene list to the ones that satisfy conditions selection framework principles will further increase specificity. Of note, this modelling is based only on automated interpretation of results, and does not account for the effect of manual interpretation. We estimate that the number of children with a finding that would be returned to families would be <1%.

The data available from the Guardian study set out in Section 3 (Background) also provides useful estimation of the likely ratio of true positive to false positive findings at the point of returning findings to families. Analysis of the first 984 participants achieved a true positive to false positive ratio of

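### The ±6% precision behind 105,000 babies belongs to the screen-positive proportion, not to the incidence of 1/572; on confirmed cases the incidence is known to about ±19% at best

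*Protocol*

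**What the plan says.** Section 6 (Sample size) of the Protocol sizes the study for precision, on one component of the primary outcome: the incidence of treatable genetic disease outside current newborn screening. The planning range is 1 in 686 to 1 in 457 live births. Of the recruitment needed for 95% certainty, it says: "the incidence estimate from the study will be between the middle point of an estimate, 1/572 +/- 6% error, is approximately 105,000".

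The next paragraph gives the inputs. The calculation uses the normal approximation to the binomial under simple random sampling, and "the proportion of subjects screened positive was assumed to be 0.011". Of that proportion it says "it was derived from an estimate of the true population incidence, the middle point of the estimate, 1/572", with 65% sensitivity and 99% specificity. Dropout is 10%. On the choice of test performance it says: "The sensitivity of detection of 65% and specificity of detection of 99% used in calculations is the lower bounds of the estimates".

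Figure 5 is described as showing a "two-sided 95% confidence interval for the proportion of subjects screened positive assuming 99% specificity and 65% sensitivity". Its caption adds: "The dotted lines indicate the expected proportion of subjects screened positive +/- 6% error margin".

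Section 10 (Modelling to guide the variant prioritisation strategy) concludes that a study-wide "specificity of 99.5% or higher is achievable". Section 13 (Interim Analysis) plans to re-evaluate the sample size for the incidence estimate by the Section 6 method with study data. It also plans to re-evaluate the number needed to reach the expected count of confirmed true positives.

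**The concern.** The sentence that states the precision and the calculation that produces 105,000 concern different quantities. The sentence puts the 6% on the incidence, 1/572 = 0.00175. The inputs and the Figure 5 caption put it on the proportion screened positive, 0.011, which is about six times larger and consists mostly of assumed false positives. A tight interval around a quantity dominated by false positives says little about the incidence.

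This is the Protocol's only formal precision statement for the primary outcome, and it is written for policy makers. A reader would conclude that the study will fix the incidence to within 6%. The same formula is carried into the interim re-evaluation of sample size, where it responds to specificity in the wrong direction.

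**Working it through.** **Inputs** (all Section 6, Sample size): incidence π = 1/572 = 0.001748; sensitivity 0.65; specificity 0.99; 95% two-sided, z = 1.96; relative error 0.06; dropout 10%.

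**1. Reproduce the stated figure.**

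- Screen-positive proportion: p = 0.65/572 + 0.01 × 571/572 = 0.001136 + 0.009983 = 0.01112, matching the stated 0.011.
- False-positive share of p: 0.009983/0.01112 = 89.8%.
- n = 1.96² × (1 − p)/(0.06² × p) = 3.8416 × 0.98888/(0.0036 × 0.01112) ≈ 94,900 evaluable.
- Divide by 0.9: about 105,450 recruited. With p rounded to 0.011 it is about 106,600.

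The stated 105,000 is reproduced, with the 6% relative to p.

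**2. Put the 6% on the incidence instead.**

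| Basis for the incidence | Evaluable | Recruited (÷ 0.9) |
|---|---|---|
| Every case found (perfect test) | 609,000 | 677,000 |
| Confirmed true positives, sensitivity known | 938,000 | 1.04 million |
| Back-calculated from p, sensitivity and specificity known | 9.37 million | 10.4 million |

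None of these is near 105,000.

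**3. Precision on incidence that 105,000 gives.** Evaluable: 105,000 × 0.9 = 94,500.

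- *Confirmed true positives.* Expected count: 94,500 × 0.65/572 = 107.4. Relative half-width: 1.96/√107.4 = 0.189, or ±19%. Interval: 0.001748 × (1 ± 0.189) = 0.00142 to 0.00208, or 1/705 to 1/481. Its width is 0.00066, against 0.00073 for the planning range (1/457 − 1/686 = 0.00219 − 0.00146).
- *Screen positives only.* SE(p) = √(0.01112 × 0.98888/94,500) = 0.000341. Dividing by sensitivity + specificity − 1 = 0.64, the half-width on incidence is 1.96 × 0.000341/0.64 = 0.001045. Relative to 0.001748 this is ±60%, or 1/1,421 to 1/358.
- *Every case found.* Expected count: 94,500/572 = 165. Half-width ±15%.

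On confirmed true positives, the relative standard error is 0.189/1.96 = 0.096. The chance of landing within ±6% is then about 47% (0.06/0.096 = 0.62 standard errors), not 95%.

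**4. How the formula responds to test performance** (recruited numbers, step 1 formula).

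| Specificity (sensitivity 65%) | N | Sensitivity (specificity 99%) | N |
|---|---|---|---|
| 98% | 55,000 | 50% | 108,000 |
| 99% | 105,500 | 65% | 105,500 |
| 99.5% | 192,000 | 100% | 99,900 |

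A lower specificity reduces N, because extra false positives raise p and make its relative error smaller. A lower sensitivity raises N slightly.

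**The case against.** The strongest reply is that nothing is hidden. Section 6 and the Figure 5 caption say openly that the calculation concerns the proportion screened positive, and Section 6 warns that such calculations depend heavily on specificity. That stands, and it makes this a wrong statement of precision, not a concealed basis. It does not rescue the sentence, because the margin is never converted to the incidence scale.

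A second reply is that updates are promised. They do not cure the problem, since Section 13 re-evaluates the incidence sample size as described in Section 6. That section does also look at confirmed true positives, which is the right basis, but against an expected count and not against a precision.

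Several stronger readings are tempting, and the Protocol does not support them:

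- *That the study will know incidence only to ±60%.* This supposes estimation from raw screen positives. Sections 12 and 13 send suspected cases for confirmatory testing and class them as apparent true positive, apparent false positive or uncertain, so about ±19% is the relevant figure.
- *That the achieved interval is wider than the planning range.* This is true only of the ±60% version. The ±19% interval is slightly narrower.
- *That any worse test lowers N.* This holds for specificity only. The 65% lower bound for sensitivity is conservative in this formula.
- *That fixing specificity at 99% when it is really 99.5% would give a negative incidence.* The 99% is a planning input. Section 13 proposes a Bayesian analysis with prior distributions on false positives and false negatives, not a fixed correction.
- *That the 6% claim runs through the document.* The Synopsis repeats 105,000 without the 6%, and Section 13 (Data analysis) speaks only of a precise estimate.

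**Conclusion.** The precision statement in Section 6 is wrong as written. 105,000 participants give ±6% on the proportion screened positive. On the incidence they give about ±19% at best from confirmed true positives, roughly three times the stated margin. Complete ascertainment of every case, including those the screen misses, would still give only ±15%.

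The ±19% rests on the Protocol's provisional 1/572 and 65%, on 94,500 evaluable babies, and on sensitivity being known without error; uncertainty in sensitivity widens it. If all 105,000 were evaluable it would be ±18%. The 1/572 counts only disorders outside current screening, and Section 13 says the expected number of true positives will be updated once the condition list is final, so the count of 107 will move.

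The lower bound for specificity is not a cautious choice here. Entering the 99.5% that Section 10 considers achievable nearly doubles the formula's N, although a more specific test makes the incidence easier to estimate. None of this shows that more babies must be recruited; it shows that the stated precision must change.

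**What to change.** Keep N. In Section 6 (Sample size), do one of two things:

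- attach the ±6% explicitly to the proportion screened positive; or
- replace it with the precision on confirmed screen-detected diagnoses: about 107 expected, about ±19%, wider once uncertainty in sensitivity is included, and conditional on the provisional 1/572 and 65%.

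The second is preferable, because it describes what the primary outcome needs. In the same section, state that the lower bound is conservative for sensitivity but not for specificity.

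In Section 13 (Interim Analysis), base the re-evaluation of the incidence sample size on the precision of the confirmed true-positive rate and drop the Section 6 screen-positive formula. The Synopsis and Section 13 (Data analysis) need only agree with the restated figure.

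The cost is a short recalculation and a wording amendment. No recruitment target changes. The price is a stated precision that looks less favourable.

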# Site selection and delivery

The study will be delivered through a select network of NHS Trust sites. The study will start with six trusts over a 4-6 month period to ensure the design of the study is working as expected before it is expanded to the number of trusts required to deliver the full sampling size. Provisional modelling has suggested that this could be up to 25-40 trusts but part of the initial implementation will involve monitoring of the consent and sample rates to identify the final number required.

Our site selection aims to ensure successful delivery of the study with a particular emphasis on ensuring diversity of participation. Criteria to determine which sites to approach to be part of the first six centered on:

- High birth volumes
- High percentage of births in hospital setting
- Level of diversity of patient reported ethnicity compared to national average
- Level of socio-economic deprivation compared to national average
- Previous engagement in the 100,000 Genomes Project, other national genomics research or the Baby and Mum Sample Study
- Track record of maternity research
- Nature of population served urban vs rural
- Support of Trust leadership to participate in the study factoring in capacity of maternity service to support recruitment

[figure not shown]
These criteria will be used to identify trusts to participate in the further implementation and scale up but a critical factor will also be ensuring we are gathering evidence in different types of trusts e.g. rural vs city, less genomically aware trusts etc.

Potential participating trusts will be approached consecutively, and invited to take part in the study. Diversity within the sample will be promoted through careful site selection, and aiming for a broadly representative sample of babies born in the country.

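### The ±6% margin assumes simple random sampling although babies come from purposively selected Trusts, so it is a best case, and the crude incidence is not shown to be that of UK newborns

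*Protocol*

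**What the plan says.** All references are to the Protocol.

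- **Section 6, Sample size.** The target is incidence in UK newborns. The text reads "The required number of participants to be 95% certain that the incidence estimate from the study will be between" limits set around the midpoint estimate, given as "1/572 +/- 6% error, is approximately 105,000". The calculation "was based on the normal approximation to the binomial distribution with simple random sampling assumed". For it, "the proportion of subjects screened positive was assumed to be 0.011", derived from 1/572 with 65% sensitivity and 99% specificity. Dropout is 10%. The Monte Carlo check, described as a "two-sided 95% confidence interval for the proportion of subjects screened positive", also draws from a single binomial.
- **Section 6, Site selection and delivery.** Delivery is through selected Trusts, approached one after another: "Provisional modelling has suggested that this could be up to 25-40 trusts". Criteria for the first six include "Level of diversity of patient reported ethnicity compared to national average", deprivation on the same footing, birth volume, research record and leadership support. They carry over to scale-up, where a mix of Trust types is also sought. The stated aim is a sample that broadly represents births in the country.
- **Section 6, Methodology and eligibility criteria.** Recruitment is in England, from mothers registered with an English GP, and covers singleton births.
- **Section 3, Analytical approach.** Sensitivity, positive predictive value and true-positive yield are expected to differ between communities. The reasons given are knowledgebase coverage, founder variants, homozygosity and condition prevalence.
- **Section 13, Interim Analysis.** Recruits' diversity is compared with births at the recruiting sites, and the sample size is re-estimated by the Section 6 method. No design effect or weighting is mentioned.

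**The concern.** The precision statement treats the babies as independent draws from one population. In the design they arrive in groups of a few thousand from Trusts picked on characteristics that the Protocol itself links to the frequency of findings. Two things follow. With groups that large, even a very small correlation within Trusts widens the interval for a wider population. And the unweighted rate describes the recruited mix of Trusts, which need not match births nationally. Both bear on how a policy maker reads the incidence figure and its margin. The simulation offered as validation cannot reveal either problem, because it makes the same assumption.

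**Working it through.** **Inputs.** From the Protocol: incidence 1/572, sensitivity 65%, specificity 99%, margin 6% (relative), dropout 10%, total 105,000, provisionally up to 25–40 Trusts. Assumed, because no intracluster correlation (ICC) is given: the between-Trust coefficient of variation (CV), and Trusts of equal size.

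**1. The plan's own figure.**
- p = 0.65/572 + 0.01 × 571/572 = 0.00114 + 0.00998 = 0.01112
- n = 1.96² (1 − p)/(0.06² p) = 94,903; divided by 0.90 this is 105,448
- With p rounded to 0.011: 95,940, then 106,600

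Both agree with about 105,000. The figure therefore reproduces with a design effect of 1, and with the 6% applied to the screen-positive proportion. False positives make up 0.00998/0.01112, about 90%, of that proportion.

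**2. Allowing for Trusts.** Evaluable babies: 105,000 × 0.90 = 94,500, so m = 3,780 per Trust (25 Trusts) or about 2,360 (40 Trusts). The simple-random-sampling margin at 94,500 is ±6.01%.
- ICC = CV² × p/(1 − p)
- Design effect DE = 1 + (m − 1) × ICC
- Margin = 6.01% × √DE

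**3. Only true incidence varies.** A change in incidence moves the screen-positive proportion by a factor of 0.65 + 0.99 − 1 = 0.64. With a CV of 30% in incidence, the between-Trust SD is 0.64 × (1/572) × 0.30 = 0.00034. That is a CV of about 3% on 0.01112.

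**4. False positives vary too.** Take an overall CV of 10% or 20% on 0.01112.

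| Overall CV on 0.011 | ICC | DE, 40 / 25 Trusts | Margin, 40 / 25 Trusts |
|---|---|---|---|
| 3% (step 3) | 0.00001 | 1.02 / 1.04 | ±6.1% / ±6.1% |
| 10% | 0.000112 | 1.27 / 1.42 | ±6.8% / ±7.2% |
| 20% | 0.000450 | 2.06 / 2.70 | ±8.6% / ±9.9% |

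**5. Confirmed cases.** p = 0.65/572 = 0.114%, so 94,500 babies yield about 107 cases. The simple-random-sampling margin is about 1.96/√107 = ±19%. At CV 20%, ICC = 0.04 × 0.00114/0.99886 = 0.000046 and DE = 1.11 (40 Trusts) or 1.17 (25 Trusts). The margin becomes about ±20%.

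**6. Population.** The named target is UK newborns. The sampled population is consented, singleton births in selected English Trusts. The planned diversity check uses births at those same Trusts. It can show uneven consent within them, but not the effect of which Trusts were chosen.

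**The case against.** The case against has several parts.

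- **Simple random sampling is declared openly, and the calculation will be updated.** True, but Section 13 re-estimates by the Section 6 method, so the assumption carries forward unless it is changed.
- **Clustered variance and standardisation belong in an analysis plan that is not at hand.** This stands as far as it goes. Section 13 announces Bayesian modelling and leaves the full strategy outside the Protocol, so their absence is not the point. The point is a stated margin that does not match the stated design.
- **The variation between communities is mainly in true disease, a tenth of the 0.011, and all samples pass through one central pipeline.** This stands and limits the size. A reader might infer that the margin is roughly doubled. That needs an overall CV near 30%, hence false positives varying between Trusts about as strongly. The Protocol allows for some such variation: it expects predictive value to differ by community and will check batch effects by recruitment site. It gives no basis for that much.
- **Trusts could be treated as fixed strata, with no inflation.** That confines inference to those Trusts, whereas Section 6 names the UK population and Appendix A asks what to expect if screening were adopted nationally.
- **The formula is approximate.** Unequal Trust sizes would raise the design effect. Recruiting a sizeable share of all Trusts would lower it. The 25–40 is itself provisional.

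**Conclusion.** The mismatch is real and its size is modest to uncertain. The ±6% is a lower bound for inference beyond the recruited Trusts. It becomes about ±6.1% if only true incidence varies between Trusts (CV up to 30%), and about ±6.8–9.9% if false positives vary as well, with an overall CV of 10–20%. These CVs are assumptions. For confirmed cases the clustering penalty is small beside a sampling margin of about ±19%.

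Two stronger readings are tempting and not supported. One is that the incidence is wrong for UK newborns. The Protocol states no over-sampling and aims for broad representativeness, so the size and direction of any shift are unknown. What can be said is that agreement with the UK population is not shown, and that England-only singleton births are a narrower population than the one named. The other is that a skewed mix of Trusts would swamp the ±6%. That compares two scales: a relative shift in incidence moves the 0.011 by only about a tenth as much (0.64/572 ÷ 0.01112 = 0.10).

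Separately, the ±6% is precision on the screen-positive proportion. Back-calculated to 1/572 with sensitivity and specificity taken as known, 94,500 babies give about ±60% even under simple random sampling. A design effect does not repair that, so the margin should not be restated as if it applied to incidence.

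**What to change.** - In Section 6, Sample size, describe ±6% as the simple-random-sampling best case for the screen-positive proportion. Set beside it a range of design effects with the assumed between-Trust variation, to be replaced by the observed value at the interim re-estimations.
- Use a Trust-clustered or Trust random-effect variance for the incidence estimate.
- Report incidence standardised to national births by ethnicity and deprivation beside the crude estimate. The Maternity Services Data Set comparison is planned only for recruiting sites, so this extends it to national birth data.
- Align the target population with what is sampled: eligible singleton births in England, with any extension to the UK argued separately.

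The cost is a slightly wider interval, access to national birth counts by ethnicity and deprivation, and a little more analysis and wording. No extra babies are needed.
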